5.5.2 Handling of Patient Withdrawals or Patient Discontinuation of Study Intervention

Patients are free to withdraw from the study or study treatment at any time. Patient participation in the study may be stopped at any time at the discretion of the investigator or at the request of the sponsor.

Patients who discontinue study treatment or active participation in the study will no longer receive study treatment. When a patient withdraws from the study, the reason(s) for withdrawal shall be recorded by the investigator on the relevant screen of the electronic case report form (eCRF). Whenever possible, all patients who discontinue study treatment or withdraw from the study prematurely will undergo all end-of-study assessments. Patients who fail to return for final assessments will be contacted by the study site (2 documented telephone calls followed by 1 registered letter or similar procedures depending on regional differences) in an attempt to have them comply with the protocol.

It is vital to obtain follow-up data on any patient withdrawn as a result of an AE or serious AE (SAE). In every case, efforts must be made to undertake protocol-specified, safety, follow-up procedures. All data collected from all patients, including early withdrawals, will be used in the reporting and analysis of the study.

5.6 Premature Termination or Suspension of Study

This study may be suspended or prematurely terminated by the sponsor. Written notification, documenting the reason for study suspension or termination, will be provided by the suspending or terminating party to the investigator, and regulatory authorities. If the study is prematurely terminated or suspended, the principal investigator will promptly inform the IRB/IEC and will provide the reason(s) for the termination or suspension.

Circumstances that may warrant termination include, but are not limited to:

- Determination of unexpected, significant, or unacceptable risk to patients.
- Insufficient adherence to protocol requirements.
- Data that are not sufficiently complete and/or evaluable.
- Determination of futility.

6 STUDY INTERVENTION

6.1 Study Product Description

ITI-007 will be supplied as 60-mg over-encapsulated tablets (capsules) (Table). The following drug supplies will be used in the study:

Table 6-1Table for Dosing Schedule

Study Treatment	Dosing Schedule
60-mg ITI-007	1 over-encapsulated tablet of 60-mg ITI-007 Daily Dose: 60-mg ITI-007
Placebo	1 over-encapsulated tablet of placebo Daily Dose: 0-mg ITI-007

ITI-007 60 mg refers to the tosylate salt (ITI-007 tosylate or lumateperone tosylate) and is equivalent to 42 mg of the active base (lumateperone).

Each ITI-007 dosing container will be labeled according to local laws and regulations. The composition of the over-encapsulated tablets is listed in Table 6-2.

6.1.1 Acquisition

Adequate supplies of ITI-007 and matched placebo will be provided to each study site.

6.1.2 Formulation, Packaging, and Labeling

ITI-007 and matching placebo will be prepared according to current Good Manufacturing Practice standards in carded blister strips and shipped under ambient conditions. Each treatment card will contain a sufficient quantity of capsules for 1 patient for two weeks (14 doses, plus 2 extras), to be dispensed every other visit of the 6-week treatment period. Each ITI-007 dosing container will be labeled according to local laws and regulations.

The dose card for each study treatment will contain two 1×8 strips of over-encapsulated tablets (final product in capsule form) as described in Table 6-.

Treatment	Card Contents
Placebo	Two 1×8 strips of placebo over- encapsulated tablets (8 over- encapsulated tablets/strip)
60-mg ITI-007	Two 1×8 strips of 60-mg ITI-007 over- encapsulated tablets (8 over- encapsulated tablets/strip)

 Table 6-3
 Bi-Weekly Treatment Cards

Note: Each card will hold 16 over-encapsulated tablets in 2 strips of 8.

6.1.3 Product Storage and Stability

Study treatment must be stored in a secure area (e.g., a locked cabinet) while in storage at the study site, protected from moisture, and kept at a room temperature between 15°C and 30°C (59°F-86°F). Patients will be instructed to store the bi-weekly treatment card at room temperature at home, out of the reach of children. Patients will be instructed to take 1 capsule per dose. Patients will be instructed to bring the bi-weekly treatment card to the study site at the next visit to assess compliance.

6.2 Dosage, Preparation and Administration of Study Product

Patients will be assigned to receive either ITI-007 (60-mg dose) or placebo. Study site personnel will receive a treatment card number from the IVRS/IWRS for each patient at every second clinic visit (e.g. at baseline and Study Days 15 and 29), to ensure that the correct investigational product is dispensed. Patients will self-administer all doses orally, once daily, at home, in the evening for the duration of the on-treatment period. Treatment will be administered with or without food, between approximately 8:00 PM and 10:30 PM, and at approximately the same time each day whenever possible. Treatments will be provided in dose cards containing 2 strips of over-encapsulated tablets. Patients will be instructed to take 1 capsule per dose. Patients will be instructed to bring the bi-weekly treatment card to the study site at the next visit to assess compliance.

6.3 Modification of Study Product Administration for a Patient

Patients who do not tolerate the study treatment should be withdrawn from the study treatment. There are no modifications of dosing allowed except withdrawal. See Section 5.5 for details regarding patient withdrawal.

An overdose is any dose of study treatment given to a patient or taken by a patient that exceeds the dose described in the protocol. Any overdose, with or without associated AEs, must be promptly reported to the Medical Monitor. Overdoses without signs or symptoms do not need to be recorded as AEs; in case of any AEs associated with the overdose, these should be reported on relevant AE/SAE sections in the eCRF.

Previous clinical trials have evaluated ITI-007 in healthy volunteers with single doses up to and including 40 mg, multiple doses up to and including 20 mg administered once daily for 5 days, and multiple doses up to and including 30 mg administered once daily for 7 days in healthy geriatric volunteers. Previous clinical trials have evaluated ITI-007 in patients with schizophrenia with multiple doses up to and including 140 mg administered once daily for 5 days, multiple doses up to and including 120 mg administered once daily for 5 days, multiple doses up to and including 120 mg administered once daily for 4 weeks, and multiple doses up to and including 60 mg administered once daily for 6 weeks. In case of an overdose that exceeds the previously studied doses, the patient should be closely monitored (in a hospital setting as needed) with sufficient attention to the symptoms and the clinical course. Supportive measures may include gastric lavage and respiratory and cardiovascular support as needed.

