9.1.10 Adverse Events

The investigator is responsible for reporting all AEs that are observed or reported during the study, regardless of their relationship to study treatment or their clinical significance.

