9.1.11 Serious Adverse Events

9.1.11.1 Definition of Serious Adverse Event

An SAE is defined as any untoward medical occurrence that at any dose:

- Results in death;
- Is life threatening;
- Requires hospitalization or prolongation in existing hospitalization;
- Results in persistent or significant disability or incapacity; or
- Is a congenital anomaly or birth defect.

The term "life threatening" refers to an event in which the patient is at risk of death at the time of the event; it does not refer to an event, which hypothetically might have caused death if it were more severe.

Medical and scientific judgment should be exercised in deciding whether an AE is serious. Some important medical events that may not result in death, be life threatening, or require hospitalization may be considered SAEs when they may jeopardize the patient such that medical or surgical intervention is needed to prevent 1 of the outcomes previously listed. Examples of such medical events include intensive emergency treatment for an allergic reaction, blood dyscrasias or convulsions that do not result in inpatient hospitalization, and the development of drug dependency or drug abuse.

Visits to urgent care or emergency room facilities may not warrant reporting as SAEs unless the patient is admitted to the hospital or the event meets other "serious" criteria. Events that are not clearly meeting "serious" criteria can be discussed on a case by case basis with the Medical Monitor to help the investigator determine whether the event meets "serious" criteria.

If either the sponsor or principal investigator believes that any event is serious, the event must be considered and evaluated by the sponsor for possible expedited reporting.

Clarification of the difference between "serious" and "severe":

The term "severe" is often used to describe the intensity (severity) of a specific event (as in mild, moderate, or severe myocardial infarction); the event itself, however, may be of relatively minor medical significance (such as a severe headache). This is not the same as "serious," which is based on patient/event outcome or action criteria usually

associated with events that pose a threat to a patient's life or functioning. Seriousness (not severity) serves as a guide for defining regulatory reporting obligations.

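### Protocol 6.3 waives AE recording for every overdose without signs or symptoms and makes no exception for intentional ones, so such an event may go unrecorded as an AE or SAE

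*Protocol*

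**What the plan says.** Protocol 6.3 defines the event by quantity only: "An overdose is any dose of study treatment given to a patient or taken by a patient that exceeds the dose described in the protocol". Intent is not mentioned. Three instructions follow:

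- Notification: "Any overdose, with or without associated AEs, must be promptly reported to the Medical Monitor".
- The waiver: "Overdoses without signs or symptoms do not need to be recorded as AEs".
- When AEs do accompany the overdose: "in case of any AEs associated with the overdose, these should be reported on relevant AE/SAE sections in the eCRF".

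The general safety sections are broader. Protocol 9.1.10 makes the investigator responsible for reporting all AEs, "regardless of their relationship to study treatment or their clinical significance". Protocol 9.1.10.1 defines an AE as any untoward medical occurrence in a treated patient and does not require a symptom. Protocol 9.1.11.1 lets important medical events be classed as serious on judgment and gives "the development of drug dependency or drug abuse" as one example. Suicide attempt and intentional overdose are not among its examples.

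On the setting, Protocol 6.2 says: "Patients will self-administer all doses orally, once daily, at home, in the evening for the duration of the on-treatment period". Protocol 6.1.2 describes the supply: "Each card will hold 16 over-encapsulated tablets in 2 strips of 8".

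**The concern.** The patients are outpatients in a major depressive episode who keep study drug at home, and suicidality is one of the stated safety objectives. In this population an intentional overdose is a suicide attempt or misuse. That is an untoward occurrence in itself, whether or not a symptom follows. Yet the only rule that deals with overdose by name releases the site from making an AE record once symptoms are absent.

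Without an AE record there is no AE-page assessment of seriousness or causality, and nothing starts the SAE reporting process in 9.4.2. The SAP's AE-based tables cannot count what was never entered. Two sites facing the same event could also handle it differently, one relying on 6.3 and the other on 9.1.10, and each could point to the protocol. With about 70 sites planned, that is a consistency problem as well as a completeness problem.

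**Working it through.** The plan gives no figure on this point, so there is nothing to reproduce. The check sets the rules side by side and follows one event through them: a patient deliberately takes more than the daily dose, has no signs or symptoms, and the site learns of it.

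**Step 1. Which rule applies?**

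- Under 6.3 it is an overdose, because the dose was exceeded. Symptoms are absent, so an AE record is not required. Intent does not change that result.
- Under 9.1.10 and 9.1.10.1 a suicide attempt or deliberate misuse is an untoward occurrence, so it is an AE and must be reported even if it has no clinical consequence.

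The two answers differ. No available passage says which prevails, exempts intentional overdoses from the waiver, or requires a suicide attempt to be entered as an AE or SAE.

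**Step 2. What is lost if the site follows 6.3?**

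- TEAE tables (SAP 16.1.1) are built from recorded AEs.
- SAE tables (SAP 16.1.2) take events marked serious on the Adverse Events page of the eCRF.
- Abuse-related tables (SAP 16.1.4) count TEAEs whose preferred terms are listed in Table D. That list names no overdose or misuse term, so even a recorded event might not be counted there.

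**Step 3. Where would the event still appear?**

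- Medical Monitor report (6.3): always required, but not linked to an AE record or to any SAP table.
- Medication-error documentation (6.5): covers too many capsules per dose, but is framed as error and is not described as AE data.
- C-SSRS (Protocol 8.1.7 and 9.1.1; SAP 16.6.5): covers suicide attempts disclosed at a visit where the scale is completed. After early withdrawal, that visit takes place only where possible (Protocol 4). The scale also collects non-suicidal self-injury, but misuse without any self-harm intent is not among its behaviors.
- SAE by hospitalization or medical judgment (9.1.11.1): possible, but 6.3 foresees a hospital setting only as needed, and the important-medical-event route is discretionary.

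**Step 4. Arithmetic for scale.**

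- Patients per arm: 350 / 2 = 175 (Protocol 12.1).
- Weight of one patient: 1 / 175 = 0.0057, or 0.57 percentage points. For k missed patients in an arm the shortfall is k × 0.57 points.
- Content of a full active card: 16 × 60 mg = 960 mg.
- Highest dose that 6.3 cites in patients: 140 mg. 140 / 60 = 2.33 capsules, so three capsules (3 × 60 = 180 mg) exceed it and bring in that section's close-monitoring sentence.

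The last line works in the plan's favor: a large intentional overdose is the kind most likely to lead to admission, and so to the SAE data. The gap is widest for overdoses that do not lead to admission.

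**The case against.** The strongest reply is that 6.3 removes a duty and forbids nothing. An investigator may still enter the event, and on a natural reading must: if the attempt or misuse is itself an untoward occurrence, it is an AE associated with the overdose, and the last clause of 6.3 sends it to the AE/SAE pages. The waiver would then cover only the excess exposure. Admission makes the event serious. The Medical Monitor hears of every overdose, and under 9.1.11.1 the sponsor or the principal investigator can each cause an event to be treated as serious. Suicide attempts also have their own data stream in the C-SSRS. Non-disclosure affects AE collection too, since 9.4 relies largely on spontaneous report and open questions, so rewording 6.3 would not cure it. Exclusion criterion 2 removes patients at significant suicide risk, and the study reference manual may contain recording instructions.

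Much of this stands. A reader might infer that asymptomatic intentional overdoses are kept out of the AE and SAE data, or that suicide attempts with study drug go unseen. The documents support neither: recording is left open rather than barred, and several other records would hold the event. Nor do they support any estimate of how many such events to expect.

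What does not stand is the claim that the general rules settle the matter. The favorable reading of 6.3 has to be supplied by the site; the sentence itself covers every symptom-free overdose. The other routes either do not feed the AE-based tables or depend on admission or individual judgment. A manual that is not part of these documents cannot be relied on to resolve a conflict inside the protocol.

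**Conclusion.** The point holds as a conflict between sections that leaves recording to site judgment. Section 6.3 waives the AE record for all overdoses without signs or symptoms; 9.1.10 and 9.1.10.1 require a report of any untoward medical occurrence. An asymptomatic intentional overdose may therefore go unrecorded as an AE or SAE at sites that follow 6.3 and be absent from the TEAE, SAE and abuse-related tables. The least protected case is symptom-free misuse without suicidal intent, which the C-SSRS would not pick up either.

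The documents do not give the number of such events. It is likely small, because the event has to be intentional, known to the site, free of symptoms, not admitted to hospital and not entered on the investigator's own judgment. Each one missed is about 0.57 percentage points of an arm, assuming about 175 treated patients per arm. The conclusion also assumes that some sites would treat 6.3 as the governing rule for overdose, and it rests on the available text, from which some sections, including the visit schedule, are missing. The correction should be made: the affected events bear directly on a stated safety objective and the remedy is cheap.

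**What to change.** Reconcile Protocol 6.3 with 9.1.10 and 9.1.11 by limiting the waiver. Suggested text:

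> Accidental overdoses without signs or symptoms do not have to be entered as AEs. Any intentional overdose (suicidal intent, misuse or abuse) is entered as an AE with or without symptoms, is assessed for seriousness, and is reported under Section 9.4.2 if serious.

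Add an overdose/misuse term to SAP Table D so that these records are counted in the abuse-related summary.

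This changes recording only. Dosing, the clinical handling of an overdose and notification of the Medical Monitor stay as they are. The cost is a short change to one protocol section, one addition to an SAP table and a few more AE records. It does not solve non-disclosure by patients.

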6.4 Accountability Procedures for the Study Product

The investigator will maintain accurate records of receipt of all test articles, including dates of receipt. In addition, accurate records will be kept regarding when and how much test article is dispensed and used by each patient in the study. Reasons for departure from the expected dispensing regimen must also be recorded. At the completion of the study, to satisfy regulatory requirements regarding drug accountability, all study treatment will be reconciled and retained or destroyed according to applicable regulations.

6.5 Assessment of Patient Compliance with Study Product Administration

Patient compliance will be assessed by capsule counts of unused study medication at each visit during the double-blind treatment phase. Any irregularities in medication adherence should be discussed with the patient. Any patient who misses 2 doses of study medication per week in any 2 weeks of the study treatment period or who misses 3 or more doses of study medication in any single week should be considered for early discontinuation. Any exceptions due to unusual circumstances should be discussed on a case-by-case basis with the Medical Monitor to determine whether a patient may continue despite apparent treatment compliance issues.

Dispensing study treatment to be taken by patients in an outpatient study increases risk for medication errors. All errors in medication dispensing or administration must be carefully documented. These errors may include but are not limited to providing the wrong dose (not taking 1 capsule per dose or taking too many capsules per dose), losing medication, or administration at the wrong time of day. Medication adherence will be emphasized at every visit. Written instructions will be provided to the patients with the weekly medication card in order to minimize medication error. Additional adherence procedures may be implemented.

6.6 Concomitant Medications/Treatments

Patients are required not to use the following during the study: alcohol, cannabis, any known 5-HT_{2A} receptor antagonist or inverse agonist, any strong or moderate cytochrome P450 3A4 inhibitor or inducer, any short-acting anxiolytic, or any drugs with known psychotropic properties or any non-psychotropic drugs with potential central nervous system effects. The only exception is zolpidem, which may be taken no more than 3 times per week, allowed only during the screening period and taken within the first 2 weeks of the treatment period (Section 5.2, Exclusion 13). Patients considered potentially eligible for participation will be required to discontinue their current antidepressant treatment and/or other psychotropic drugs for the duration of the study.

Discontinuation of long-acting prohibited medications that require more than a 2-week washout should be discussed on a case-by-case basis with the Medical Monitor for approval of a longer screening phase to ensure washout of excluded medication with longer half-life (e.g., fluoxetine) under the supervision of the investigator before baseline.

Acetaminophen (Paracetamol) use is prohibited, but ibuprofen is allowed.

Use of all concomitant medications will be recorded in the patient's eCRF. As a minimum requirement, the drug name and dates of administration are to be recorded. This will include all prescription drugs, herbal products, vitamins, minerals, and over-the-counter medications. Any changes in concomitant medications will also be recorded in the patient's eCRF.

Any concomitant medication deemed necessary for the welfare of the patient during the study may be given at the discretion of the investigator. However, it is the responsibility of the investigator to ensure that details regarding the medication are recorded in full in the eCRF.

7 STUDY SCHEDULE

Before participating in any study procedures, all potential study patients must sign an informed consent form (ICF). Patients will have the opportunity to have any questions answered before signing the ICF. The investigator must address all questions raised by the patient. The investigator will also sign the ICF and a signed copy will be provided to the patient.

The schedule of events for the study is presented in Appendix A. Detailed instructions for the conduct of study assessments and procedures will be provided in the study reference manual.

-	
-	

-	
—	
_	

-	
_	
ī	

8 STUDY PROCEDURES /EVALUATIONS

8.1 Study Procedures/Evaluations

After obtaining written informed consent, the following assessments are to be performed within 2 weeks prior to Day 1 (unless the Medical Monitor has approved an extended screening period to allow washout of prior long-acting psychotropic medication), according to the schedule of events in Appendix A; assessments can be conducted on different days within the screening period.

8.1.1 Informed Consent

Before any study-related activities the patient must sign and date an ICF approved by the responsible IRB/IEC. The format and content of the ICF must have been agreed upon by the investigator, the appropriate IRB/IEC, and ITI.

8.1.2 Medical History and Other Information

Medical history information will be collected at screening and should include (but not be limited to) demographic information, current and past medical conditions, and current and past medications. The medical history must be documented in the patient's study chart prior to study treatment administration and also recorded in the appropriate eCRF. In addition to conventional medical history, information pertaining to the patient's average alcohol and caffeine consumption and average tobacco and cannabis usage should be recorded in the eCRF.

Patients will be checked for previous participation in an ITI-007 clinical study and for duplicate enrollment by study site staff using any methods available for identifying duplicate patients.

